12.10.2. Analyses of Key Secondary Efficacy Endpoint(s)

Secondary efficacy variables include the following 2 key secondary endpoints with alpha-protection. The treatment effect of lonapegsomatropin compared with placebo will be tested for the alpha-protected secondary endpoint using a fixed sequence testing procedure described in Section 12.10.3.

- Change from baseline in total body lean mass at Week 38 (as assessed by DXA)
- Change from baseline in trunk fat mass at Week 38 (as assessed by DXA)

For the statistical method of analyzing the secondary endpoints, the ANCOVA model described in Section 12.10.1 will be repeated for the total body lean mass and trunk fat mass. The absolute values and mean change from baseline at each timepoint and at Week 38 for all secondary efficacy endpoints will be presented by treatment group.

In addition, correlation will be evaluated for the change from baseline in trunk fat mass and total body lean mass with the change in IGF-1 SDS level at Week 38.

Comparative statistics (p-values, 95% CI for differences) will be provided for the treatment comparison of lonapegsomatropin with placebo for all secondary efficacy endpoints. The 95% confidence intervals will be calculated for the mean treatment differences between lonapegsomatropin vs. placebo and lonapegsomatropin vs. daily somatropin.

12.10.3. Multiplicity Adjustment

A fixed-sequence testing procedure will be applied to control the family-wise error rate at a level of 0.05 ([Guidance for Industry 2017](#)). Under this testing procedure, the key secondary efficacy endpoints will be tested only if the superiority of primary efficacy endpoint of trunk percent fat for lonapegsomatropin over placebo is met at a two-sided 0.05 significance level. If the p-value for the primary endpoint is < 0.05 , then the 2 key secondary endpoints listed below will be tested sequentially as below:

Test 1: Change from baseline in total body lean mass at Week 38

Test 2: Change from baseline in trunk fat mass at Week 38 (will be tested only if the result of Test 1 is significant $P < 0.05$)

12.10.4. Sensitivity Analyses

To assess the robustness of the primary analysis, the following sensitivity analyses of the primary endpoint will be performed.

Sensitivity Analysis 1

Analysis of the primary endpoint will be repeated in the per-protocol population.

Sensitivity Analysis 2

Analysis of the primary endpoint will be repeated for all subjects in the ITT Population who completed 38 weeks of trial treatment regardless of intercurrent event and have a DXA assessment within final assessment window between study day 240-295.

Sensitivity Analysis 3

To assess the impact of randomized subjects using different stratification factors across dosing groups and regions, analysis of the primary endpoint will be repeated for ANCOVA model which only includes treatment arm, region (Japan versus other countries), and dosing group and baseline trunk percent fat as covariates.

Sensitivity Analysis 4

The tipping point analysis will be conducted by iteratively assigning plausible outcomes to missing values for subjects in different treatment group independently until the conclusion is reversed (eg, analyses are no longer statistically significant). The same analysis method for the primary analysis as specified in Section 12.10.1 will be applied when analyzing adjusted data generated under each plausible shift parameter. The set of shift parameters, K_1 and K_2 , will be selected to explore the space of possible missingness assumptions systematically and comprehensively. K_1 and K_2 are chosen such that the means are shifted to reduce the treatment effect and to identify the point where the p-value is tipped to be insignificant ($P >= 0.05$) (Little 2002, Rubin 1987).

The steps for conducting tipping point analysis using PROC MI are described below:

Step 1: The pre-specified set of shift parameters are K_1 for lonapegsomatropin group and K_2 for placebo group. K_1 is a set of shift parameters lying between 0 to 10 and K_2 is a set of shift parameters lying between -10 to 0. Let $k_1 \in K_1$ and $k_2 \in K_2$. Start the tipping point algorithm assuming $k_1=0$ and $k_2=0$ (under the MAR assumption, an additional step will be performed to fill in the intermittent missing data to obtain a dataset with only monotone missing pattern before implementing PROC MI using the MONOTONE option)

Step 2: For each k_1 and k_2 , impute missing data conditional on k_1 and k_2 using PROC MI to form 100 complete datasets. The variable list for imputations will include region (North America, Europe, Asia), dosing group and AGHD onset (adult vs. childhood), results from baseline and post baseline values for trunk percent fat.

Step 3: Given the shift parameters (k_1, k_2), conduct pre-specified statistical analysis as described in Section 12.10.1 for each of the 100 complete datasets and integrate the results across 100 datasets by Rubin's rule using PROC MIANALYZE.

Step 4: In the event that the tipping point is not identified using the pre-specified set of shift parameters K_1 and K_2 , extend K_1 to include additional shift parameters between 10 and 20 and extend K_2 to include additional shift parameters between -20 and -10. Repeat steps 2-3 utilizing the additional shift parameters until the tipping point is identified or all possible pairs have been analyzed.

Imputed P-values from the analysis described above will be graphically presented as a heat-map to demonstrate two dimensional tipping point between the 2 treatment groups (Lonapegsomatropin vs. Placebo).

12.10.5. Analyses of Subgroup

Subgroup analyses of the primary efficacy endpoint using the ANCOVA model will be repeated to determine whether treatment effects are consistent across clinically meaningful subgroups.

[figure not shown]
The difference in change from baseline at Week 38 in trunk percent fat and their 95% confidence intervals will be displayed in a Forest Plot. Subgroups will include but not limited to, the subgroups outlined in [Table 3](#).

Table 3: Planned Subgroup Analyses

[figure not shown]
Subgroup Name	Subgroup Levels
Region	North America, Europe, Asia-Pacific; All regions except Japan vs. Japan;
Diabetes mellitus status (at baseline)	Yes, No
Age (years)	< 30, ≥ 30 - ≤ 60, > 60
Sex	Male, Female
AGHD Onset	Adult, Childhood
BMI (kg/m ²)	< 30, ≥ 30
Concomitant oral estrogen at screening for female	Yes, No
Dosing Group	Group 1: Oral estrogen intake (any age) or < 30 years old Group 2: ≥ 30 to ≤ 60 years old; no oral estrogen intake Group 3: > 60 years old; no oral estrogen intake
Race	American Indian or Alaska Native Asian Black or African American Native Hawaiian or Other Pacific Islander White Other
Ethnicity	Hispanic or Latino Not Hispanic or Latino Not Reported Unknown

Some subgroups maybe collapsed when there is small number of subject in the category

12.10.6. Analyses of Tertiary Efficacy Endpoints

12.10.7. Analyses of Exploratory Efficacy Endpoints

12.11. PHARMACODYNAMICS AND PHARMACOKINETICS

12.11.1. Pharmacokinetics

The analysis of PK endpoints will be based on the PK/PD analysis set.

Serum concentration values below the limit of quantification (BLQ) will be set to zero when calculating summary statistics; hGH baseline-corrected values which are negative will be set to zero. Baseline-corrected concentrations will be derived by subtracting individual's baseline (i.e. pre-dose at V1) from each trial visit:

$$[\text{baseline-corrected serum concentration data}] = [\text{Visit X}] - [\text{baseline (i.e. V1 pre-dose)}]$$

hGH (absolute and baseline-corrected), lonapegsomatropin and mPEG serum levels (ng/mL) will be summarized by dosing group and visit using descriptive statistics (number of subjects, arithmetic mean, arithmetic SD, arithmetic CV, median, minimum, and maximum, if applicable) and box plot will be presented.

12.11.2. Pharmacodynamics

The analysis of PD endpoints will be based on the PK/PD analysis set.

All serum concentration values BLQ will be set to lower limit of quantification when calculating summary statistics; baseline-corrected values which are negative will be reported as negative values. Baseline-corrected concentrations will be derived by subtracting individual's baseline (i.e. pre-dose at V1) from each trial visit: $[\text{baseline-corrected serum concentration data}] = [\text{Visit X}] - [\text{baseline (i.e. V1 pre-dose)}]$.

Absolute and baseline-corrected serum concentration data will be listed and summarized by time point for using descriptive statistics (number of subjects, arithmetic mean, arithmetic SD, arithmetic CV, median, minimum, and maximum, if applicable). The absolute values and changes from baseline in IGF-1 (ng/mL), IGF-1 SDS, IGFBP-3 and IGFBP-3 SDS will also be analyzed by visit using an ANCOVA models and descriptive summary by dosing groups will be provided.

Box plot of IGF-1, IGFBP-3, IGF-1 SDS and IGFBP-3 SDS serum concentration data (absolute and baseline-corrected).

In addition, the proportion of subjects with IGF-1 SDS level categories will be summarized at each timepoint.

12.12. SAFETY ANALYSIS

The safety analysis will be performed using the Safety Analysis Set. The safety parameters will include adverse events (AEs), clinical laboratory, vital sign, electrocardiographic (ECG) parameters, MRI, fundoscopy, immunogenicity and other safety parameters if collected. For safety endpoints, all analyses will be based on the observed data (i.e., with no imputation of missing data), unless otherwise stated.

12.12.1. Adverse Events

Adverse events will be coded by system organ class (SOC) and preferred term (PT) using the Medical Dictionary for Regulatory Activities (MedDRA) Version 26.0 (the most current March version of the dictionary).

An AE (classified by preferred term) will be considered a treatment emergent adverse event (TEAE) if it occurred on or after the first dose of investigational product and was not present prior to the first dose, or it was present at the first dose but increased in severity during the trial through 14 days after the last dose of treatment on the main period or the date of first dose on the extension period whichever occurs first.

- Summary of TEAEs by treatment
- TEAEs by treatment, SOC and PT (sorted by descending frequency by SOC and PT)
- TEAEs by treatment, SOC and PT Reported by > 5% of subjects in any treatment group
- Related TEAE by treatment, SOC and PT
- Serious TEAEs by treatment, SOC and PT (sorted by descending frequency by SOC and PT)
- Serious Related TEAEs by treatment, SOC and PT (sorted by descending frequency by SOC and PT)
- AEs leading to death by treatment, SOC and PT (sorted by descending frequency by SOC and PT)
- TEAEs leading to discontinuation of trial by treatment, SOC and PT (sorted by descending frequency by SOC and PT)
- TEAEs leading to discontinuation of treatment by treatment, SOC and PT (sorted by descending frequency by SOC and PT)
- TEAEs by treatment and PT (sorted by descending frequency of PT)
- Related TEAEs by treatment and PT (sorted by descending frequency of PT)
- Serious TEAEs by treatment and PT (sorted by descending frequency of PT)
- Deaths by treatment

Detailed listings for all AEs, serious TEAEs, AEs leading to the discontinuation of trial, TEAEs leading to the discontinuation of treatment, AEs leading to death and special situation will also be generated.

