12. ADVERSE EVENTS, SERIOUS ADVERSE EVENTS, AND REPORTING

12.1. ADVERSE EVENTS

12.1.1. Definition of Adverse Event (AE)

An AE is defined as any untoward medical occurrence in a clinical investigation subject administered a pharmaceutical product and which does not necessarily have a causal relationship with the treatment. An AE can arise with any use (eg, in combination with another drug), route of administration, formulation, or dose, including an overdose. An AE can therefore be any of the following:

- Any unfavorable and unintended sign (including an abnormal laboratory finding), symptom, or disease temporally associated with the use of a medicinal (investigational) product, whether or not related to that product.

- AEs not previously observed in the subject that emerge during the protocol-specified AE reporting period, including signs or symptoms associated with GHD that were not present prior to the AE reporting period.
- Complications that occur as a result of protocol-mandated interventions (e.g. invasive procedures, blood sampling).
- If applicable, AEs that occur prior to assignment of study treatment associated with medication washout, no treatment run in, or other protocol-mandated interventions.
- Preexisting medical conditions (other than the condition being studied) judged by the investigator to have worsened in severity or frequency or changed in character during the protocol-specified AE reporting period.

Based on the nonclinical and clinical program to date, the risks associated with the use of lonapegsomatropin are anticipated to be the same as those seen with daily somatropin products. Possible AEs associated with somatropin therapy are listed in the current Investigator Brochure which will serve as the reference for safety information for lonapegsomatropin.

For complete information regarding clinical safety of the daily somatropin products, please refer to the Product Prescribing Information.

Clinically significant treatment-emergent abnormal findings from physical examination, laboratory abnormalities, and worsening of pre-treatment conditions may be recorded as AEs.

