12.3.2. Recording Procedures for All Adverse Events

All AEs will be documented in response to questions about the subject’s well-being and whether any possible changes in well-being have occurred since the previous visit. Additionally, at each visit, site staff will review subject diary data with the subject, to determine if diary entries reflect any AEs.

AEs, including SAEs, will be documented through the end of the subject’s participation in the trial or Early Termination visit. All AEs must be recorded on the appropriate CRF. AEs either observed by the investigator or reported by the subject must be recorded regardless of causality. The following attributes must be documented for each reported AE:

- Subject ID
- AE Term
- Description (for SAEs)
- Onset date (if AE was present on Day 1, include whether onset was prior to or after the first dose of the study drug)
- Resolution date, if applicable
- Severity

- Causality (relationship to the study drug)
- Outcome
- Action taken
- Determination of “seriousness criteria” (whether serious or not serious)

Any medical history condition, signs, symptoms, and illnesses active during the Screening Period will be captured as baseline (pre-existing) events, if appropriate, to assure that any change(s) in these experiences during the trial also are recorded as an AE and a complete safety profile is obtained. An event that occurs after signing of ICF but prior to the first study drug administration will be documented as medical history unless the event is trial procedure-related, in which case it will be reported as a non-treatment-emergent AE. Any new or worsening pretreatment event that occurs from the time of the first study drug administration until the last visit will be recorded as an AE.

Routine titration of chronic, concomitant medications will not be considered to meet the criteria for AEs. In addition, increased IGF-1 levels requiring study drug dose decrease (ie, IGF-1 SDS > 2.0) will not be considered as AE. However, occurrence of clinically significant symptoms/conditions associated with increased IGF-1 levels will be considered as AE.

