Investigators should use correct medical terminology/concepts when reporting AEs or SAEs. Avoid colloquialisms and abbreviation (e.g., hypertension for elevated blood pressure that persists and requires chronic treatment and follow-up, or increased blood pressure for elevated blood pressure that occurs for a limited time and does not persist or require ongoing treatment).

AEs will be documented at the maximum intensity experienced. If a previously recorded and closed AE or condition recorded as part of medical history increases in severity or frequency, it will be recorded as a new AE.

All AEs will be considered ongoing until they have completely resolved or are deemed stable or commensurate with ongoing disease processes by the investigator. At study completion or the Early Termination Visit, all AEs should have a statement regarding resolution, see also Section 10.2.4 and Section 10.2.5.

An accidental overdose is not an AE if there are no signs or symptoms. Any undesirable medical occurrence resulting from an accidental overdose is an AE and should be recorded and reported on the appropriate eCRF. Regardless of classification as an AE or not, *all* overdoses should be documented, and the subject(s) monitored. Since accidental overdoses with the study drug could have serious clinical consequences and/or represent a compliance issue, they should be reported to the Medical Monitor immediately and evaluated by the Sponsor. See Section 12.1.3.

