- Hospitalization or prolonged hospitalization for diagnostic or elective surgical procedures for pre-existing conditions
- Hospitalization or prolonged hospitalization required to allow efficacy measurement for the study
- Hospitalization or prolonged hospitalization for scheduled therapy of the target disease of the study.

Pre-existing Medical Conditions

A pre-existing medical condition is one that is present at the start of the study. Such conditions should be reported as medical and prior procedures. A pre-existing medical condition should be re-assessed throughout the trial and reported as an AE or SAE only if the frequency, severity, or character of the condition worsens during the study. When reporting such events, it is important to convey the concept that the preexisting condition has changed by including applicable descriptors (e.g., worsening type 2 diabetes mellitus).

Pregnancy

If a female subject becomes pregnant while receiving the study drug or within 2 weeks after the last dose of study drug, or if the female partner of a male study subject becomes pregnant while the study subject is receiving the study drug, a Pregnancy report form should be completed and expeditiously submitted to Sponsor. Follow-up to obtain the outcome of the pregnancy should also occur and the outcome reported to Sponsor. DXA scans cannot be performed on subjects who are pregnant or suspected to be pregnant.

Abortion, whether accidental, therapeutic, or spontaneous, should always be classified as serious, and expeditiously reported as an SAE. Similarly, any congenital anomaly/birth defect in a child born to a female subject exposed to the study drug should be expeditiously reported as an SAE.

Product Complaints

A Product Complaint is defined as any written or oral information received from a complainant that alleges deficiencies related to identity, quality, safety, strength, purity, reliability, durability, effectiveness, or performance of a product after it has been released and distributed to the commercial market or clinical trial.

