11.2.3. Missing Dates in Adverse Events

For determination of treatment-emergent adverse event (TEAE), if the start date and time of an AE are partially or completely missing, the AE will be assumed to be treatment-emergent if it cannot be definitely shown that the AE did not occur or worsen on or after the first dose in the trial (worst case approach).

The following rules will be used for TEAE determination where the AE has a missing start date.

If the start time of an AE is missing, but the start date is complete, an AE will only be excluded from treatment-emergent AEs if the start day is before day of first treatment or the start day is after end of study day.

If the start time and day are missing but the start month is complete, an AE will only be excluded from treatment emergent AEs if the start month is before the month of first treatment or the start month is after the end month of end of study month or if the stop date/time is before the start of first treatment date.

If the start day and month are missing but the start year is complete, an AE will only be excluded from treatment-emergent AEs if the start year is before year of first treatment or if the start year is after end of study year or if the stop date/time is before the start of first treatment.

If the start date is completely missing, an AE will not be excluded from treatment emergent AEs unless the stop date/time is before the start of first treatment.

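### The SAP's TEAE definition leaves out some events the protocol records as adverse events, and conflicts with the SAP's own missing-time rule

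*SAP*

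**What the plan says.** SAP 12.12.1 opens with the timing and the level of comparison: "An AE (classified by preferred term) will be considered a treatment emergent adverse event (TEAE) if it occurred on or after the first dose". It then adds that the event must be one that "was not present prior to the first dose, or it was present at the first dose but increased in severity during the trial". The window closes 14 days after the last main-period dose or at the first extension dose, whichever comes first.

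The protocol's criteria for recording an AE are wider:

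- Protocol 12.1.1 includes pre-existing conditions "judged by the investigator to have worsened in severity or frequency or changed in character".
- Protocol 12.3.3 says a pre-existing condition is to be "reported as an AE or SAE only if the frequency, severity, or character of the condition worsens during the study".
- Protocol 12.3.2 says that if a closed AE or a "condition recorded as part of medical history increases in severity or frequency, it will be recorded as a new AE".
- Protocol 12.3.2 also says that an event between consent and first dose "will be documented as medical history unless the event is trial procedure-related".

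SAP 11.2.3 covers missing AE dates and times. Where the date is complete but the time is missing, "an AE will only be excluded from treatment-emergent AEs if the start day is before day of first treatment" or after the end of study. Its general principle refers to an AE occurring or worsening, and does not limit worsening to severity.

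**The concern.** The SAP offers two routes into the TEAE tables: the term was absent before dosing, or it was present at the first dose and became more severe. The protocol treats frequency and character as further grounds for recording an AE, and neither has a route. Nor does a condition that was present before dosing, had gone by the first dose, and then came back worse.

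Safety and tolerability is secondary objective 1. Protocol 14.4.4 promises AE incidence by system organ class and preferred term, and the SAP delivers almost all of that as TEAE tables. Protocol section 14 makes the final SAP the analysis of record, so its definition decides which events are tabulated.

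Severity alone is a thin test here. Protocol Table 6 grades it by disruption of daily activity. The protocol's own example of a worsened condition is type 2 diabetes, which can worsen without a change in that grade. The severity comparison also lacks a stated baseline. Most pre-dose events go to medical history, while the protocol lists severity as an attribute of AEs.

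**Working it through.** The plan states no figure on this point, so there is none to reproduce. The check applies each rule as written to the possible event types.

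| Event on treatment | Protocol requires an AE record? | TEAE under SAP 12.12.1, literal | TEAE under SAP 11.2.3, start time missing |
|---|---|---|---|
| New term | Yes | Yes | Yes |
| Ongoing at first dose, severity rises | Yes | Yes | Yes |
| Ongoing at first dose, only frequency or character worsens | Yes (12.1.1, 12.3.3; frequency also 12.3.2) | **No** | Yes |
| Resolved before dosing, returns at higher severity or frequency | Yes (12.3.2) | **No** | Yes |
| Resolved before dosing, returns unchanged | Only through the general AE definition in 12.1.1 | No | Yes, if recorded |
| Ongoing and unchanged | No | No | No |

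The last column assumes an AE record with a start date on or after first treatment and not after end of study. Rows three and four are the finding: the protocol requires a record, 12.12.1 excludes it, and 11.2.3 includes it.

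**How often 11.2.3 would apply.** The AE attributes listed in Protocol 12.3.2 include an onset date, and for events present on Day 1 whether onset was before or after the first dose. No onset time is listed. If the eCRF follows that list, the missing-time rule could cover most AEs.

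**Illustration of scale.** The documents give no prevalence or recurrence rates, so every rate here is an assumption. For one preferred term and 80 subjects per arm, let:

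- h = share of subjects with the term before dosing (5% to 40%);
- r = share of those with an on-treatment event that fails 12.12.1 (10% to 50%);
- i = incidence in subjects without the term before dosing (10%).

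Incidence with all events counted is (1 − h)·i + h·r. Incidence counted under 12.12.1 is (1 − h)·i. The omission is 80·h·r subjects.

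- h = 5%, r = 10%: 80 × 0.05 × 0.10 = 0.4 subjects.
- h = 10%, r = 30%: all events 0.90 × 0.10 + 0.10 × 0.30 = 12.0% (9.6 of 80); counted 9.0% (7.2 of 80); omitted 2.4.
- h = 40%, r = 50%: 80 × 0.40 × 0.50 = 16 subjects.

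Under 11.2.3 the omission is 0 for the same records. The range is too wide to serve as an estimate; it shows only that the choice of rule can matter.

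**End of window.** SAP 12.12.1 stops at 14 days after last dose or at the first extension dose; SAP 11.2.3 stops at end of study. Protocol 12.2.1 ends AE reporting 2 weeks after the last dose or at study discontinuation, if earlier. Note c of the Schedule of Events ends it at Visit 7 for subjects entering the extension. Few events should fall between the two limits. Some might, because Protocol 12.3.2 documents AEs to the end of participation and Protocol 8.2 keeps subjects who stop drug on the visit schedule.

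**The case against.** The strongest reply is that the problem largely removes itself. If most AEs have no start time, the date-only rule in 11.2.3 decides them, and it has no prior-presence test. This is fair, and it is why the finding is a conflict between two rules. It does not settle the matter. The protocol's attribute list is not the eCRF, and 11.2.3 itself speaks of start date and time. A programmer could also read 11.2.3 as a timing rule only, with the prior-presence test in 12.12.1 still applied on top.

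A second reply is that the SAP never says AEs are compared with medical history. A worsened condition is entered as a new AE, and that record did not exist before dosing, so on a record-level reading it is a TEAE. That reading is possible, and some worsened conditions may also code to a different preferred term. But the definition says it works by preferred term, so the literal text points the other way and the derivation is left to interpretation.

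A third reply is that the affected events are not lost. The all-AE listing keeps them. AEs leading to death, deaths and injection site reactions are not worded as TEAE-only, and laboratory, vital-sign and ECG summaries do not depend on TEAE status. This stands and limits the consequence. Safety reporting is descriptive, and no efficacy result is touched.

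A reader might also infer that same-severity recurrences are protocol AEs that the SAP drops. The documents do not firmly support that. Protocol 12.3.2 and 12.3.3 speak of new or worsened events, and only the general definition in 12.1.1 could bring such a recurrence in.

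**Conclusion.** The point holds as a mismatch and an internal conflict. Followed literally, SAP 12.12.1 leaves out of the TEAE tables pre-existing conditions that worsen in frequency or character only, and conditions resolved before dosing that return at higher severity or frequency. The protocol requires both to be recorded. SAP 11.2.3 would count the same records whenever start time is missing.

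This rests on two assumptions: that prior presence is judged by preferred term, as the text says, and that the medical-history record counts as prior presence, which the SAP does not state.

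It would go too far to say that the safety tables will undercount, or that the lonapegsomatropin-placebo contrast will shrink by a given amount. The first depends on which SAP rule is applied. The second needs event rates by arm that the documents do not contain. The end-of-window difference is a minor alignment issue.

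**What to change.** Before unblinding, replace the definition in SAP 12.12.1 with one at the level of the AE record. Suggested wording:

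*A TEAE is any recorded AE with onset, or with worsening in severity, frequency or character, on or after the first dose and up to 14 days after the last main-period dose or the first extension dose, whichever is earlier.*

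Then:

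- Drop the preferred-term condition on absence before the first dose. The protocol's specific recording rules already limit on-treatment records to new or worsened events.
- State that a condition resolved before dosing and later recorded as a new AE is classified by the onset date of that record.
- In SAP 11.2.3, use the same end date as 12.12.1 whenever the start date is complete. Let the Day 1 before-or-after-dose item in Protocol 12.3.2 settle events on the day of first dose.

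The cost is SAP wording and one programmed derivation, with no new data collection. The downside is that TEAE counts may rise slightly in every arm.
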